1.3.2.2. Nonclinical Toxicology of florbetaben

Animal studies have not been performed to evaluate the carcinogenic potential of florbetaben. Florbetaben did not demonstrate mutagenic potential in an in vitro bacterial mutation assay (Ames test) using five strains of Salmonella typhimurium and one strain of Escherichia coli or in an in vitro chromosomal aberration assay using human peripheral lymphocytes in the absence and presence of a metabolic activator. No study on impairment of male or female fertility and reproductive performance was conducted in animals.

1.4 Clinical Data to Date

1.4.1. Human Experience with ¹¹C-ER176

1.4.1.1. Safety data for ¹¹C-ER176

Nine healthy volunteers had 11 C-ER176 injected for whole-body PET scans (1 man and 2 women; mean age \pm SD, 30 ± 10 y) [20]. Eight separate healthy volunteers had 11 C-ER176 injected for brain PET imaging (1 man and 2 women; 32 ± 9 y old). 11 C-ER176 was intravenously injected over 3 min. Specific activity was 121 ± 64 GBq/ μ mol at the time of injection.

No adverse or clinically detectable pharmacologic effects were observed with ¹¹C-ER176 for any of the 17 subjects. No significant changes in vital signs or electrocardiograms were observed during the PET scan or in the results of laboratory tests repeated after the scan.

1.4.1.2. Whole body imaging with ¹¹C-ER176 in human subjects

Nine healthy volunteers participated in the whole-body PET scans (1 man and 2 women each with HAB, MAB, and LAB status; mean age \pm SD, 30 ± 10 y)[20]. TSPO affinity type was determined by in vitro receptor binding to TSPO on leukocyte membranes or genetic analysis. Time–activity curves were derived from volumes of interest for each source organ (i.e., brain, heart, lungs, liver, spleen, kidneys, and thyroid) delineated on the whole-body images using PMOD. For whole-body images, the measured radioactivity in each organ was converted to SUV. Regional SUV averaged from 60 to 120 min after injection (SUV60–120 min) was used to

measure radioligand uptake in each organ. This period was used because it better reflects receptor binding than the early period, which is strongly affected by blood flow. Differences in SUV60–120 min for each organ were compared between genotypes by Kruskal–Wallis testing.

Whole-body imaging clearly showed that the in vivo binding of 11 C-ER176 was sensitive to rs6971. Uptake for brain and lung was lower in LABs than in HABs at all time-points, with intermediate values for MABs. SUV60–120 min showed a significant difference between genotypes in heart (P < 0.05). The same tendency was observed in brain, lung, and spleen (Table 1).

Table 1. Organ Uptake of ¹¹C-ER176 for Each Genotype[20] Organ uptake

Organ	HABs $(n = 3)$	MABs $(n = 3)$	LABs (n = 3)	P
Brain	1.3 ± 0.1	1.0 ± 0.1	0.8 ± 0.1	0.05
Thyroid	2.8 ± 1.2	1.4 ± 0.4	1.3 ± 0.2	0.11
Lung	2.2 ± 0.3	1.5 ± 0.5	0.9 ± 0.1	0.06
Heart	6.8 ± 0.3	5.0 ± 0.6	3.5 ± 0.9	0.04
Liver	3.0 ± 0.7	3.3 ± 0.3	2.8 ± 0.1	0.25
Spleen	4.3 ± 0.1	3.7 ± 0.8	2.7 ± 0.3	0.06
Kidney	3.9 ± 0.4	3.6 ± 0.3	2.5 ± 0.2	0.10

Data are mean $SUV_{60-120 \text{ min}} \pm SD$. *P* values were derived from Kruskal–Wallis test between genotypes.

Residence times were calculated directly using the "Residence Times" model implemented in PMOD. Absorbed radiation doses were calculated by entering the residence times for each source organ into OLINDA/EXM, version 1.1, using the model for a 70-kg adult man. The residence time of organs was calculated for the 9 subjects. The effective dose was 4.1 \pm 0.4 $\mu Sv/MBq$, which is similar to that of other ^{11}C -labeled radioligands.

1.4.1.3. Brain imaging with ¹¹C-ER176 in human subjects

Eight separate healthy volunteers with either HAB, MAB, or LAB status had brain PET scans with 11 C-ER176 (1 man and 2 women each for HAB and MAB status and 2 men with LAB status; 32 ± 9 y old) [20]. TSPO affinity type was determined by in vitro receptor binding to TSPO on leukocyte membranes or genetic analysis. The 3 HABs who participated in the brain PET scans received an oral dose of 90 mg of the TSPO agonist N-benzyl-N-ethyl-2-(7-methyl-8-oxo-2-phenylpurin-9-yl)acetamide (XBD173) as a partial blockade about 1.75 h before the second injection of 11 C-ER176.

For brain images, total volume of distribution (V_T) , an index of receptor density that equals the ratio at equilibrium of the concentration of radioligand in tissue to that in plasma, was calculated with 1- and unconstrained 2-tissue compartment models (2TCM and 1TCM, respectively) using the radiometabolite-corrected plasma input function. To determine the minimal scan length for reliable measurements and also to indirectly assess whether ^{11}C -ER176

radiometabolites enter the brain, the time stability of V_T was examined by increasingly truncating the 90-min scan by 10-min increments to the shortest length of 0–50 min.

A modification of the Lassen plot was used to estimate V_{ND} of $^{11}\text{C-ER176}$ in brain in 2 ways: with an occupancy plot using the difference in V_T at baseline and after partial blockade with XBD173 in HABs, and with a polymorphism plot using the difference in V_T between 2 genetic groups (i.e., between HABs and MABs, between HABs and LABs, and between MABs and LABs).

Brain time–activity curves fitted better with 2TCM than 1TCM. The unconstrained 2TCM fitting converged in brain time–activity curves from all regions, in all scans, and in all genotypes, both at baseline and after blockade with XBD173 in HABs (Fig. 4A). Compared with the 1TCM, the 2TCM showed lower mean Akaike information criterion scores (130 vs. 242) and higher mean model selection criterion scores (6.4 vs. 2.9). An F test also showed that the goodness of fit was significantly better with the 2TCM than with the 1TCM in all 154 fittings over a total of 11 scans, indicating the presence of significant amounts of both specific and nonspecific binding in human brain. The 2TCM identified V_T well, with an average SE of 2.4% across brain regions. Regional V_T values (mL·cm-3) were consistent with the known distribution of TSPO, showing high levels in the brain stem (4.3) and low levels in the putamen (3.2) at baseline for HABs.

After receiving XBD173, all 3 HABs showed marked blocking effects, both in brain and in plasma. That is, receptor blockade decreased peak uptake in brain, increased washout, and decreased total uptake over the 90-min scan (Fig. 1A). In plasma, XBD173 significantly increased the concentration of ¹¹C-ER176, consistent with its blocking the distribution of the radioligand to organs of the body (Fig. 1B)

[figure not shown]

Fig. 1. Brain uptake and plasma radioactivity concentrations (conc) of 11 C-ER176 in representative HAB at baseline (\circ) and after blockade with 90 mg of XBD173 (\bullet).

 V_T values were stable from 60 to 90 min and were well identified (SE < 10%) in all 3 genotypes with the exception of 1 MAB and in the 3 HABs after blockade, which had low specific binding like that in LABs, indicating negligible accumulation of radiometabolites regardless of the genotype.

 V_T values were higher for HABs than for LABs in all regions of interest, with intermediate values for MABs. The whole-brain V_T in HABs (3.3 \pm 0.9 mL·cm-3) was about 1.2-fold higher than that in MABs (2.9 \pm 0.9 mL·cm-3) and about 2.2-fold higher than that in LABs (1.6 \pm 0.5 mL·cm-3). V_T for 11 C-ER176 was well identified by the 2TCM in all genotypes.

The receptor blocking study using XBD173 found that $^{11}\text{C-ER176}$ had adequately high BP_{ND} for all genotypes. The whole brain BP_{ND}—without correcting for f_P—was 4.2 ± 1.3 and 1.4 ± 0.8 for HABs and LABs, respectively. The high BP_{ND} and good identifiability in all genotypes, including LABs, suggests that this new radioligand would likely have better sensitivity in detecting abnormalities in patients and that LABs may not need to be excluded as they are for $^{11}\text{C-PBR28}$.

In summary, although ¹¹C-ER176 does not show sensitivity to the rs6971 SNP in vitro (see Section 8.1.1.), this radioligand does show a small degree of sensitivity to the SNP in vivo. This in vivo sensitivity is seen in both brain and peripheral organs (see Section 9.2.). However, the difference in binding between HABs and LABs is much lower for ¹¹C-ER176 than for ¹¹C-PBR28. Importantly, V_T and BP_{ND} may be reliably quantified in LABs with ¹¹C-ER176.

1.4.2. Human Experience with ¹⁸F-florbetaben

Human brain studies with ¹⁸F-florbeteben have been performed (see Package Insert). The results are summarized as follows. ¹⁸F-florbetaben was evaluated in three single arm clinical studies (Study A-C) that examined images from adults with a range of cognitive function, including some end-of-life patients who had agreed to participate in a post-mortem brain donation program. Subjects underwent ¹⁸F-florbetaben injection and scan, then had images interpreted by independent readers masked to all clinical information. The Standard of Truth (SoT) was based on the histopathologic examination using Bielschowsky silver staining (BSS) of six brain regions assessed by a Pathology Consensus Panel masked to all clinical information (including PET scan results). ¹⁸F-florbetaben PET imaging results (negative or positive) corresponded to a histopathology derived plaque score based on the Consortium to Establish a Registry for Alzheimer's Disease (CERAD) criteria using neuritic plaque counts. For the subject level SoT, if in any of the six regions β amyloid neuritic plaques were more than sparse, the subject was classified as positive; if in none of the regions the β-amyloid neuritic plaques were assessed as being more than sparse, the subject was classified as negative.

Study A evaluated 18 F-florbetaben PET images from 205 subjects and compared the results to postmortem truth standard assessments of brain β -amyloid neuritic plaque density in subjects who died during the study. The median age was 79 years (range 48 to 98 years) and 52% of the subjects were male. By medical history 137 study participants had AD, 31 had other non-AD dementia, 5 had dementia with Lewy Bodies (DLB), and 32 had no clinical evidence of dementia. Interpretation of images from 82 autopsied subjects was compared to the subject level histopathology SoT. Three readers, after undergoing in-person tutoring, interpreted images using a clinically applicable image interpretation methodology. At autopsy, the subject level brain β amyloid neuritic plaque density category was: frequent (n = 31); moderate (n = 21); sparse (n = 17); or none (n = 13).

In Study B five independent, blinded readers underwent the Electronic Media Training in the clinically applicable image interpretation methodology and assessed images from the same 82 end-of-life subjects who enrolled in Study A. The time interval between the 18F-florbetaben

scan and death was less than one year for 45 patients, between one and two years for 23 patients and more than two years for 14 patients.

Study C evaluated the reliability and reproducibility of the clinically applicable image interpretation methodology using the Electronic Media Training; 461 images from previous clinical studies were included from subjects with a range of diagnoses. Five new readers assessed randomly provided images from subjects with a truth standard (54 subjects who underwent an autopsy) and without a truth standard (51 subjects with mild cognitive impairment, 182 subjects with AD, 35 subjects with other dementias, 5 subjects with Parkinson's Disease and 188 healthy volunteers). Among the 461 subjects, the median age was 72 years (range 22 to 98), 197 were females, and 359 were Caucasian. Interreader agreement across all 5 readers had a kappa coefficient of 0.79 (95% CI 0.77, 0.83). The performance characteristics in 54 subjects with SoT were similar to those measured in Studies A and B. Additionally, intra-reader reproducibility was assessed from 46 images (10%); the percentage of intra- reader agreement for the 5 readers ranged from 91% to 98%.

1.5 Dose Rationale and Risk/Benefits

Based on prior human experience and dosimetry data, we expect the proposed injected activity of ¹¹C-ER176 (up to 20 mCi) to be safe without expected toxicity. ¹⁸F-florbetaben is an FDA-approved radiopharmaceutical used here for research purposes at injected activity recommended by the manufacturer (up to 8.1 mCi).

2 Study Objectives

This is a proof-of-concept study to determine if ¹¹C-ER176, a novel and improved radioligand for TSPO, detects increased TSPO density in patients with Alzheimer's disease. ¹⁸F-florbetaben will be used to confirm Alzheimer's disease pathophysiology in the patient group. We also seek to determine the test-retest reliability of ¹¹C-ER176 in humans.

We propose to inject ¹⁸F-florbetaben in 50 human subjects, each as a one-time dose, as part of the screening process. Twenty-five subjects will be cognitively normal. Twenty-five subjects will have either mild cognitive impairment or Alzheimer's disease.

From the screened subjects, we propose to inject ¹¹C-ER176 in 30 human subjects, each as a one-time dose, as part of the screening process. Fifteen subjects will be cognitively normal. Fifteen subjects will have either mild cognitive impairment or Alzheimer's disease.

In four of the control subjects, we will perform test-retest ¹¹C-ER176 imaging. Each subject will have two injections of ¹¹C-ER176 for the test-retest study.

3 Study Design

3.1 General Design

3.1.1. Subject recruitment and screening procedures

Men and women age 50 and older will be recruited from the Columbia Doctors Aging and Dementia clinic, the CUMC Alzheimer's Disease Research Center (ADRC), [name] Questionable Dementia 2 (QD2) cohort, and the CUMC Washington Heights-

Inwood Community Aging Project (known locally as WHICAP, R01 AG037212, PI [name]). Participants may also co-enroll from the cognitive aging studies of [name] (protocol AAAO9758) and [name] (protocols AAAI2752, AAAQ8249, and AAAQ8096), and from CUMC protocols AAAO1151, AAAQ7868, and AAAR4352 (PI = [name]). Participants may also self-refer as this study will be registered on clinicaltrials.gov. Informed consent will be obtained prior to study enrollment.

For subjects with cognitive impairment, prior to obtaining informed consent, a licensed physician who is not listed as personnel on this protocol will determine whether the subjects has capacity to provide their own consent. If the subject lacks consent, a legally authorized representative will be required to provide consent for the subject. Only subjects who can provide an understanding of the study procedures, particularly of the risk of pain associated with the arterial catheter placement, by providing verbal assent, may be enrolled via the surrogate consent process. Subjects who are unable to provide meaningful assent will not be enrolled into the study.

Up to 50 subjects will undergo screening including history, physical examination, routine laboratory studies, neuropsychological testing, brain MRI, and amyloid PET imaging.

If any of the above screening procedures have been performed within one year of the ¹¹C-ER176 PET scan visit, then those procedures will not need to be repeated under this protocol. Rather the previously obtained results will be used.

Subjects will be categorized as either amyloid-positive or amyloid-negative on PET. Subjects will be identified as either cognitively normal or cognitively impaired in consensus conference. Subjects must have Clinical Dementia Rating scale score of 0.5 or above and meet clinical criteria for either amnestic MCI (single or multiple-domain)[25] or Alzheimer's disease[26] to be included in the cognitively impaired category. Of the screened subjects, only amyloid-positive patients and amyloid-negative controls will undergo ¹¹C-ER176 PET.

Subjects will have genetic analysis to determine the presence of the rs6971 (Ala147Thr) SNP on the TSPO gene.

Target sample size for completers is 15 amyloid-positive patients and 15 amyloid-negative controls (30 subjects total). Our enrollment goal of 25 subjects per group will allow a 40% general screen failure/drop-out rate. Subjects who are coenrolled in other CUMC studies will not need to have brain MRI under this protocol if done within the last 12 months. Coenrolled subjects will not need to have ¹⁸F-florbetaben PET under this protocol if 1) they are controls and have had a negative ¹⁸F-florbetaben or other amyloid PET scan within the previous 12 months, or 2) they are patients and have ever had a positive amyloid PET scan using any amyloid radioligand (¹⁸F-florbetaben, ¹⁸F-florbetapir, ¹⁸F-flutemetamol, or ¹¹C-Pittsburgh Compound B).

3.1.2 Neuropsychological testing

The diagnosis of MCI or AD will be based on updated criteria[25, 26]. The neuropsychological test battery will include the following tests: the Mini-Mental State Examination, Selective Reminding Test, Benson Complex Figure Copy and Recall, MINT, Rosen Drawing Test, single word and sentence repetition from the NACC FTD module,

Geriatric Depression Scale (15 items), Trail Making Tests A and B, and Verbal Fluency (CFL, and Animals). Raw scores and demographically corrected T-scores (age, years of education, sex, and ethnicity) will be determined.

3.1.3. Imaging procedures

One brain MRI will be performed on each subject using a 3T scanner. Sequences performed will include 3D T1 (MPRAGE, 180 slice 1 mm resolution, 256 x 256 voxel count) for volumetric analysis and clinical sequences to exclude subjects with other intracranial pathology unrelated to AD. PET scans will take place on a Biograph mCT PET scanner (Siemens Healthcare) at the CUMC Kreitchman PET Center. Subjects will have one ¹⁸F-florbetaben (Neuraceq) PET scan (up to 8.1 mCi) to determine amyloid status[27]. Subjects will have one PET scan with ¹¹C-ER176 (injected activity 10-20 mCi), except for 4 controls who will have two ¹¹C-ER176 scans for test-retest imaging. ¹¹C-ER176 imaging will be performed with arterial sampling. ¹¹C-ER176 will be synthesized by the CUMC PET Department Radiochemistry Laboratory. ¹⁸F-Florbetaben will be purchased from Piramal Imaging. Subjects will be informed if a clinically important abnormality is detected on PET imaging (e.g., brain tumor).

Prior to 11 C-ER176 PET imaging, one arterial catheter and one intravenous catheter will be placed. After a low-dose CT scan for attenuation correction, up to 20 mCi 11 C-ER176 will be injected intravenously over 3 minutes. Emission scan will begin at the start of the radioligand infusion according to the following frame schedule: 30 seconds x 6, 1 minute x 3, 2 minutes x 2, and 5 minutes x 16 for total scan time of 90 min. During the emission scan, arterial samples will be drawn at 10 second intervals for the first 4 min using an automated blood sampler. Thereafter, manual arterial samples will be drawn at 6, 8, 10, 15, 20, 30, 40, 50, 60, 75, and 90 minutes. Alternatively, manually samples may be drawn at 15 sec intervals for the first 2.5 min, then at 3, 4, 6, 8, 10, 15, 20, 30, 40, 50, 60, 75, and 90 minutes. Radioactivity in plasma will be quantified by a γ -counter and analyzed by reverse-phase chromatography to separate parent radioligand from radiometabolites[43] by the PET center radiometabolite laboratory. Free fraction of 11 C-PBR28 in plasma (f_P) will be measured by ultrafiltration and normalized using a standard derived from pooled donor plasma[44]. Because one aim is to determine if 11 C-ER176 may be useful in AD studies using simplified analysis, some subjects may have 11 C-ER176 imaging without arterial catheterization .

3.1.4 Image processing

FreeSurfer (http://surfer.nmr.mgh.harvard.edu/), the MRI software package comprising a suite of automated tools for segmentation, reconstruction, and derivation of regional volumes and surface-based rendering, will be used for derivation of regions-of-interest (ROIs). Eleven ROIs will be extracted from the structural T1 image: entorhinal cortex, hippocampus, inferior temporal cortex, combined superior and middle temporal cortex, superior parietal lobule, inferior parietal lobule, precuneus, occipital cortex, prefrontal cortex, striatum, and thalamus. Age-adjusted hippocampal volumes will be used to define the presence or absence of neurodegeneration[28]. A single static ¹⁸F-florbetaben image acquired 50-70 min post-injection will be read by a trained investigator blinded to the subject's diagnosis ([name]). A visual binary read (positive or negative) will be determined according to criteria established by Piramal imaging to stratify subjects as amyloid-positive or amyloid-negative.

¹¹C-ER176 PET images will be analyzed using Freesurfer. ROIs will be applied to coregistered PET images to generate time-activity curves. The metabolite-corrected plasma activity curve will be used to estimate rate constants using the one- and two-tissue compartment models using PMOD software. The total distribution volume will be calculated from the resulting rate constants.

3.1.5. Blood sampling and analysis

Subjects will undergo venipuncture to collect 70 mL of blood. Collected blood will be used for screening laboratories, and for research tests. Research tests include determination of *TSPO* genotype, determined by SNP analysis using polymerase chain reaction with a pre-existing Taqman assay[17, 18, 29] in the Biomarkers Shared Resource of CUMC. Blood will also be collected for genetic and non-genetic tests related to inflammation (e.g., TREM2, use of peripheral blood mononuclear cells to create monocyte-derived microglia-like cells). Results from research tests will not be released to participants. Approximately 20 mL of blood sampled will be used for screening tests and approximately 50 mL of blood will be used for research tests. Blood samples will be stored prior to research use in a secure freezer. Stored samples will be labeled with subject ID number and no personal identifying information will be included on the stored sample label. Because the first eight participants to enter this study only had blood drawn for screening tests and *TSPO* genotyping, these subjects will be asked to return for another study visit to have 50 mL of blood drawn for research tests. Such returning participants will be re-consented prior to having the 50 mL blood draw.

3.2 Primary Study Endpoints

Because the drugs used in this study are radioligands given at tracer doses, there are no clinical endpoints of the study.

Comparing PET imaging among groups

PET images will be analyzed using 1) the two-tissue kinetic model to calculate total distribution volume, corrected for free fraction of radioligand in plasma (V_T/f_P), and 2) the cerebellum as a pseudo-reference region to calculate standardized uptake value ratios (SUVR). Effect size will be calculated for different regions as the difference in means (AD vs. controls) divided by the standard deviation.

Secondary outcomes

3.3 Secondary Study Endpoints

Coefficient of variation (%COV = standard deviation / mean) will be calculated for controls and patients with AD for both $V_{\rm T}/f_{\rm P}$ and SUVR data. SUVR values will be calculated using cerebellum as reference regions. Additional reference regions will be explored. Correlation coefficients will be computed to look for correlation between 11 C-ER176 binding and clinical severity. We will also look for correlations between 11 C-ER176 binding and atrophy, as

determined using ROI volumes derived from MRI data. We will also calculate test-retest reproducibility for ¹¹C-ER176 using data from the 4 controls who have two ¹¹C-ER176 scans.

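### No partial-volume correction is planned, so atrophy would tend to lower apparent binding in patients and tie a region's binding to its own volume

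*Combined protocol and SAP*

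**What the plan says.** Section 3.1.4 (Image processing) derives eleven regions from the T1 MRI with FreeSurfer. The list begins "entorhinal cortex, hippocampus, inferior temporal cortex, combined superior and middle temporal cortex". For the tracer scan, "ROIs will be applied to coregistered PET images to generate time-activity curves", and compartment models are fitted to those curves.

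Sections 3.2 and 7.2 define the two outcome measures: V_T/f_P from the two-tissue model, and SUVR with the cerebellum as pseudo-reference. The primary summary is: "Effect size will be calculated for different regions as the difference in means (AD vs. controls) divided by the standard deviation".

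Section 3.3 and the synopsis add a correlation of binding with atrophy, "determined using ROI volumes derived from MRI data". Section 7.2 does not mention this correlation. The only adjusted volume in the plan is in Section 3.1.4: "Age-adjusted hippocampal volumes will be used to define the presence or absence of neurodegeneration". It serves to classify neurodegeneration and is not linked to the correlation.

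The corrections that the plan names are for attenuation, plasma metabolites and plasma free fraction. Partial-volume correction is not mentioned in any section.

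**The concern.** A PET scanner blurs the image. A thin or small region loses counts to its surroundings, and the loss grows as the region shrinks. None of the named corrections deals with this. V_T scales with the tissue curve, so lost tissue signal passes into V_T, and f_P is a plasma quantity. SUVR escapes only if target and cerebellum lose the same fraction.

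The loss is unlikely to be equal in the two groups. Under Section 3.1.1, scanned patients are amyloid-positive and impaired (CDR 0.5 or above), while controls are amyloid-negative and cognitively normal. The plan itself treats atrophy as something that varies among subjects, since it classifies neurodegeneration and correlates binding with atrophy.

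Two results are at stake. The regional effect size, which is the primary output and is meant to inform a larger study, would be biased downward. The binding-atrophy correlation would share an error source on both axes and could hide a true pattern of more inflammation where there is more atrophy.

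**Working it through.** **Plan's own figure.** There is none on this point. The only sample-size arithmetic, 15/(1 − 0.40) = 25 screened per group, reproduces and is not involved.

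**Inputs from the documents.** 15 patients and 15 controls (Section 3.1.1). Whole-brain V_T in HABs 3.3 ± 0.9 (Section 1.4.1.3), from three HABs in a sample aged 32 ± 9 years. COV = 0.9/3.3 = 27.3%.

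**Assumed inputs.** Cortex 2.5 mm thick; scanner FWHM 4 to 6 mm; CSF signal 0; white matter w = 0.5 to 0.7 of cortical signal; thinning of 10% (to 2.25 mm) or 20% (to 2.0 mm). The documents give none of these.

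**Step 1: signal loss in a cortical slab.** With σ = FWHM/2.355 and Φ the normal distribution function, mean apparent signal over a slab of thickness T is

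A(T) = (1/T) ∫₀ᵀ [Φ(x/σ) − Φ((x−T)/σ) + w·Φ(−x/σ)] dx, and loss L = 1 − A(T_thin)/A(2.5).

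For w = 0.5 and FWHM 4 mm: A(2.5) = 0.6252, A(2.25) = 0.5971, A(2.0) = 0.5666. So L = 1 − 0.5971/0.6252 = 4.5% and 1 − 0.5666/0.6252 = 9.4%.

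| w | FWHM (mm) | Loss, 10% thinning | Loss, 20% thinning |
|---|---|---|---|
| 0.5 | 4 | 4.5% | 9.4% |
| 0.5 | 5 | 4.6% | 9.5% |
| 0.5 | 6 | 4.6% | 9.3% |
| 0.7 | 4 | 3.6% | 7.5% |
| 0.7 | 5 | 3.6% | 7.5% |
| 0.7 | 6 | 3.5% | 7.2% |

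With w = 0 the losses are 7.5–8.8% (10% thinning) and 15.6–17.9% (20%).

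**Step 2: shift in d when there is no true difference.** Shift ≈ −L/COV.
- 10% thinning: 3.5/27.3 = 0.13 to 4.6/27.3 = 0.17.
- 20% thinning: 7.2/27.3 = 0.26 to 9.5/27.3 = 0.35.

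**Step 3: effect on an assumed true d of 0.8.** Apparent d = [(1 + d·COV)(1 − L) − 1] / [COV·√((1 + (1−L)²)/2)].
- COV 27.3%: 0.66 at L = 3.5%, 0.39 at L = 9.5%.
- COV 15% (assumed): 0.55 and 0.10.

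**Step 4: induced correlation.** Assume that each region's binding is paired with its own volume, true binding is unrelated to volume, and apparent binding = true binding × volume^k. Assume also volume COV 12% and patient atrophy 15–20%. If slab volume is proportional to thickness, Step 1 implies k between ln(0.928)/ln(0.8) = 0.33 and ln(0.954)/ln(0.9) = 0.45. Simulation at binding COV 27.3%, 20,000 trials per setting:

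| k | Mean r, 15 patients (p < 0.05) | Mean r, all 30 (p < 0.05) |
|---|---|---|
| 0 | 0.00 (5%) | 0.00 (5%) |
| 0.25 | +0.10 to +0.11 (6–7%) | +0.13 to +0.15 (11–12%) |
| 0.50 | +0.21 (12%) | +0.25 to +0.29 (29–35%) |

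A positive r here means less binding where there is less tissue.

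**The case against.** **The size is almost wholly assumed. This stands.** The documents give no scanner resolution, expected atrophy or regional SD in elders. The result also depends on the model. Adding an opposite sulcal bank 1 mm away gives 1.6–2.7% loss for 10% thinning if the gap stays fixed, and 7.5–8.8% if it widens to 1.5 mm. A cortical slab does not represent hippocampus, striatum or thalamus. The direction assumes that a region's surroundings carry less signal than the region itself.

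**The denominator is weak. This stands.** It is whole-brain V_T, not regional V_T/f_P or SUVR, in three young volunteers. With n = 3, the 95% interval for an SD of 0.9 runs from about 0.47 to 5.7. SUVR is not quantified at all, and loss in the cerebellum could partly cancel there.

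**The shift is small beside sampling error, in a descriptive pilot. This stands in part.** The standard error of d at 15 versus 15 is about √(2/15) = 0.37, larger than any shift in Step 2. Section 7.1 disclaims power, and no decision rule is stated. An observed increase would not be undermined, because the bias runs against it. But Section 7.1 excuses imprecision, not bias, and more subjects in the later study would not remove the bias.

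**Two stronger readings are tempting and not supported.** A reader might infer that the correlation uses volumes unscaled for head size. Section 3.3 says only ROI volumes; it does not exclude scaling, and does not state that each region is paired with its own volume. A reader might also infer that the effect size will fall below zero. That needs a true effect smaller than the shift, or a large loss. For a true d of 0.8, a negative value (−0.34) appeared only with an assumed 15% loss and an assumed 15% COV.

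**Conclusion.** The point holds as a directional bias of unknown size. Followed as written, the plan measures regional binding without correcting for spill-out in groups that can be expected to differ in atrophy. That tends to lower V_T/f_P in patients, and SUVR unless the cerebellum loses signal equally. It works against the primary objective, and where a region is paired with its own volume it pushes the Section 3.3 correlation toward less binding with more atrophy.

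The illustrative size of 0.13 to 0.35 in d rests on the slab assumptions and on one small, young, whole-brain sample; it should not be quoted as an estimate for this trial. The documents do not support a claim that the trial will report a false negative. The practical harm is that a null or reversed uncorrected result in an atrophic region could not be interpreted. The plan should be changed, but the point does not invalidate the design. Head-size scaling is unspecified and is a separate, minor matter; it would not correct partial-volume loss.

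**What to change.** - **Section 3.1.4:** name one MRI-based partial-volume correction that uses the planned FreeSurfer labels, and state the scanner resolution it assumes. Fix both before the PET data are analysed, so that the choice cannot follow the results.
- **Sections 3.2, 3.3 and 7.2:** report regional effect sizes (V_T/f_P and SUVR) and binding-atrophy correlations both uncorrected and corrected. Keep the uncorrected analysis, because correction adds noise. Add the atrophy correlation to Section 7.2.
- **Interpretation, Section 7.2:** state that a null or reversed uncorrected result in an atrophic region will not be read as absence of increased TSPO without the corrected result beside it.
- **Clarification, Section 3.3:** state whether each region's binding is paired with its own volume, in which subjects, and whether volumes are scaled for head size.

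The cost is analysis time on MRI and PET data already planned, and a second set of noisier estimates to report. No new subject, scan or procedure is needed.
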